4.4. Successes in Research Implementation

4.4.1. Pilot Study on Naltrexone with Prisoners. In our pilot study conducted in Maryland prisons,¹² we achieved three main objectives: 1) we demonstrated that formerly opioid-dependent prisoners would accept XR-NTX treatment, beginning in prison; 2) strengthened our collaboration with the Maryland Division of Correction (DOC) custodial and medical staff by establishing logistics with correctional staff regarding XR-NTX administration; and 3) worked out logistics with our community treatment provider in terms of in-prison and community treatment, thus assuring continuity of care from prison to the community.

4.4.2. Recruitment and Follow-up of Drug-Involved Research Participants. We have been exceptionally successful in obtaining voluntary consent and cooperation of individuals with OUD to participate in research projects. In our previous study of methadone treatment for prisoners, 99% of eligible clients consented to participate, and over 95% of 1-, 3-, 6-, and 12-month post-release interviews were completed.^{43,45-47} In our study of Buprenorphine for Prisoners, we have achieved follow-up rates exceeding 92% of study participants at 1-, 3-, 6-, and 12-months after release from prison. In our study of XR-NTX for Probationers/Parolees, we have achieved follow-up rates over 90% at 6-, 12-, and 18-months. In our ongoing study involving HIV testing of parolees/probationers, we consented over 2000 probationers/parolees for testing and 100 for our HIV-positive intervention study; follow-up rates are 95% for each of our follow-up periods (1-, 6-, 12-, and 15-months).

5.0 SPECIFIC APPROACH

5.1. Maryland Department of Public Safety and Correctional Services (MDPSCS)

Male and female inmates recruited for participation will be drawn from the following seven prisons: 1) Brockbridge Correctional Facility (BCF); 2) Dorsey Run Correctional Facility (DRCF); 3) Baltimore City Correctional Center (BCCC); 4) Maryland Correctional Institution (MCIW) for Women; 5) Central Maryland Correctional Facility (CMCF) 6) Maryland Correctional Training Center (MCTC); and 7) Roxbury Correctional Institution (See **Letter of Support** from MDPSCS). The seven facilities are administered by the Maryland Division Department of Correction (DOC), and are staffed by administrative and custodial personnel and by case managers, who provide referral services and are responsible for preparing reports concerning inmates' institutional progress and adjustment. MDPSCS and FRI investigators have an extensive history of collaborating on pharmacotherapy studies for opioid-dependent prisoners.

5.2. Participant Eligibility: Inclusion/Exclusion Criteria

Eligible inmates must meet the following criteria: (1) adult male or female inmate at BCF, DRCF, BCCC, MCIW, CMCF, MCTC, or RCI and be eligible for release within 30 days; (2) history of opiate disorder [meeting DSM-V criteria of dependence at the time of incarceration; individuals who do not meet criteria at time of incarceration and become addicted during incarceration will be eligible]; Inmates not meeting the opioid-dependence criterion will be eligible if they were treated in an opioid agonist treatment program during the year before incarceration. (3) suitability for XR-NTX treatment as determined by medical evaluation; (4) currently opioid-free by history, with negative urine for all opioids and no signs of opiate withdrawal; (5) willingness to enroll in XR-NTX treatment in prison [not currently in or planning to pursue agonist (methadone, buprenorphine) treatment at release]; and (6) planning to live in Baltimore City or County (individuals outside of Baltimore City/county will be allowed to participate as long as they agree to travel to the treatment clinic if randomized to OTX). Inmates with one or more of the following conditions will be excluded from the study: (1) Liver function test levels greater than three times normal (note: if a blood specimen is unable to be drawn the individual will not be excluded from participation); (2) Active medical illness that may make participation hazardous (e.g., unstable diabetes, heart disease). Adequately treated medical conditions are acceptable; (3) Untreated psychiatric disorder that may make participation hazardous (e.g., untreated psychosis, bipolar disorder with mania). Adequately treated psychiatric disorders and appropriate psychotropic medications will be allowed; (4) History of allergic reaction to XR-NTX; (5) Current chronic pain diagnosis for which opioids are

prescribed; (6) creatinine above normal limits; (7) pregnancy (for women); (8) Breast-feeding (for women) (9) suicidal ideation (within the past 6-months); and (10) Body Mass Index (BMI) > 40.

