Subjects:	Inclusion Criteria: (1) adult male or female inmate at BCF, DRCF, BCCC, MCIW CMCF, MCTC, or RCI and be eligible for release within 30 days; (2) history of opiate disorder [meeting DSM-5 criteria of dependence at the time of incarceration; individuals who do not meet criteria at time of incarceration and become addicted during incarceration will be eligible]. Inmates not meeting the opioid-dependence criterion will be eligible if they were treated in an opioid agonist treatment program during the year before incarceration (3) suitability for XR-NTX treatment as determined by medical evaluation; (4) currently opioid-free by history, with negative urine for all opioids and no signs of opiate withdrawal; (5) willingness to enroll in XR-NTX treatment in prison [not currently in or planning to pursue agonist (methadone, buprenorphine) treatment at release]; and (6) planning to live in Baltimore City or County (individuals planning to live outside of Baltimore City/county will be allowed to participate as long as they agree to travel to the treatment clinic if randomized to OTX. Exclusion Criteria: (1) Liver function test levels greater than three times normal (if a blood sample is not obtained at baseline participants will still be eligible for participation); (2) Active medical illness that may make participation hazardous (e.g., unstable diabetes, heart disease). Adequately treated medical conditions are acceptable; (3) Untreated psychiatric disorder that may make participation hazardous (e.g., untreated psychosis, bipolar disorder with mania). Adequately treated psychiatric disorders and appropriate psychotropic medications will be allowed; (4) History of allergic reaction to XR-NTX; (5) Current chronic pain diagnosis for which opioids are prescribed; (6) creatinine above normal limits; (7) pregnancy (for women); (8) Breast-feeding (for women); (9) suicidal ideation (within the past 6-months); and (10) Body Mass Index (BMI) > 40
Study Product:	Vivitrol ® (naltrexone for extended release injectable suspension) 380 mg per month delivered in monthly intramuscular injections
Duration:	7 months (1 injection in prison and 6 in the community.
Sample Size:	240 subjects
Statistical Methodology:	A Generalized Linear Mixed Model (GLiMM) will be used to conduct all analyses.

List of Abbreviations

Abbreviation/specialist term	Explanation
XR-NTx	Long acting naltrexone
DSM-V	Diagnostic and Statistical Manual of Mental Disorders, Fifth Edition

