
5.7.3. Missed XR-NTX Injections. Participants who miss a monthly appointment will be contacted by the study RA within 24 hours of missing their appointment. The participant will be strongly encouraged to receive their next injection. If they miss a dose and return for a subsequent dose more than 7 days after their missed scheduled injection they will receive the following: 1) drug use questionnaire; 2) urine rapid test; and 3) naloxone challenge before the naltrexone injection. Everyone who reports opioid use or has a positive urine test for opioids during days 29-37 will be given the naloxone test and then the oral naltrexone (12.5mg) prior to the Vivitrol injection. If a participant misses a scheduled injection, he/she will have up to 37 days to receive their next XR-NTX injection. We will also record the number of successful rescues and number of delayed returns to XR-NTX treatment. Participants will no longer receive XR-NTX if they become incarcerated in jail or prison (if incarcerated less than 37 days, they will still be eligible receive their injection).

5.7.4. Withdrawal from Naltrexone: Treatment Safety. Participants may voluntarily stop taking XR-NTX doses at any time without penalty. Naltrexone is an opioid antagonist with no opioid agonist properties and no withdrawal upon discontinuation. Potential side effects relate to the medication itself and to the injection. The most frequent side effects of the medication include opioid withdrawal symptoms for those participants who still have some trace of opioids in their system. There had been reports of increased liver enzymes in individuals receiving high doses of oral NTX in a study of obesity. For this reason, we have an exclusion criterion regarding elevated liver function tests at baseline. The injection can lead to local irritation, infection, and potentially abscesses, which in the most extreme circumstance may require surgical debridement. Participants receiving XR-NTX who require acute treatment of pain will be told that they need to inform their physicians that they are on XR-NTX because XR-NTX is an antagonist and will block the effects of opioid-agonist pain medications. In addition, each participant will also receive a laminated card that indicates they are on XR-NTX that can be provided to their health care provider.

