5.8.5. Opioid Overdose Scale. This self-administered questionnaire will ask participants to report the number of opiate overdoses where they did and did not receive medical attention. The questionnaire administered at baseline will cover the period prior to the instant incarceration while the questionnaire follow-up in the community, will cover post-release months 1-12.

5.8.6. Visual Analogue Scale (VAS). Participants are asked to place a mark across the line at the point that corresponds to their immediate craving for opioids. Anchors included 0 mm – ‘no cravings’ to 100 mm – ‘most

extreme cravings possible'.^{94,95} Participants will be assessed at baseline and at each follow-up visit and asked about peak cravings during the preceding 24 hours.

5.8.7. Health-related quality of life will be measured by the EuroQol 5D (EQ-5D).^{108, 109} The preference weights obtained from the EQ-5D will be used to calculate quality-adjusted life-years (QALYs; see section D.4). The EQ-5D is the most widely used generic, preference-based health-related quality of life instrument.¹¹⁰

5.8.8. Official Records. As in our previous research,⁹⁶ official record data will be obtained from the MDPSCS at 12-months. Data will include type (e.g., charges involved) and number of arrests, convictions, and incarcerations; and the number and length of time of each imposed disciplinary period. Criminal record data will be used to assess the validity of self-report criminal activity data.

5.8.9. Biometric Measures. All participants will complete the following biometric measures for inclusion/exclusion criteria, participant monitoring, and serious adverse event (SAE) and adverse event (AE) reporting. The following biometric measures will be completed (see **Figure 3**): 1) history and physical; 2) liver function tests (note: if a blood specimen is unable to be drawn the individual will not be excluded from participation), hepatitis profile; 3) vital signs; 4) concomitant medications; 5) pregnancy, 6) HIV; 7) Urine toxicology; and 8) AEs.

5.8.10. Data Management/Quality Control. Assessments will be administered by trained RAs, and closely supervised by the PI. RAs will receive training concerning: (a) initiating and developing rapport; (b) sensitivity regarding culture, gender, and sexual orientation; (c) forms administration; (d) serious adverse event reporting; (e) responsibility for maintaining participant confidentiality; and (f) follow-up procedures.

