	Baseline in prison	1mo	2mo	3mo	4mo	5mo	6/7mo
Biometric Measures (for inclusion/exclusion criteria, patient monitoring and AE determination)							
History & Physical	✓						✓ (7only)
Liver Function Tests, Hepatitis Profile	✓						✓ (7only)
Vital signs	✓	✓	✓	✓	✓	✓	✓
Concomitant medication	✓	✓	✓	✓	✓	✓	✓
Pregnancy	✓	✓	✓	✓	✓	✓	✓
HIV	✓						✓ (7only)
Urine toxicology	✓	✓	✓	✓	✓	✓	✓
Adverse Events	✓	✓	✓	✓	✓	✓	✓

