9.2. Protection Against Risks

9.2.1. Risks Associated with XR-NTX. Participants may experience symptoms of opioid withdrawal from the naloxone challenge, oral naltrexone, or XR-NTX injection. In order to minimize the likelihood of withdrawal symptoms, potential participants will be carefully screened with exclusion criteria which include recent opiate use history and a urine test prior to naloxone administration. The study design was carefully crafted to minimize risk of withdrawal by first administering the short-acting naloxone followed by a small oral dose of naltrexone prior to XR-NTX administration. Individuals who do experience opiate withdrawal symptoms from the administered opioid antagonists will be treated symptomatically by the study’s medical personnel.

To protect against risks of increase in liver enzymes, study applicants will be excluded if their liver enzymes are greater than triple the normal levels. Also, liver enzyme tests will be repeated during the course of the study and doses withheld if indicated.

Participants will be warned of the risk of opioid overdose should they discontinue XR-NTX and will be informed of alternative treatment, including methadone or buprenorphine treatment. Finally, participants will be informed that they should carry their study identification card with them and provide it to any medical personnel that will be treating them in the future so they can be aware of the need to provide appropriate alternatives to opioids for pain relief.

The study physician has extensive experience in the injection technique. This should minimize the likelihood of injection site reactions. Nonetheless, the FDA has provided the following information for healthcare professionals with regard to Naltrexone Injection Site Reaction [naltrexone for extended-release injectable suspension (marketed as Vivitrol)] FDA Alert [08/12/08] Vivitrol injections may be followed by pain, redness, itching, bruising, and swelling. Sometimes reactions at the injection site can quickly worsen and skin and other tissue can be permanently damaged and require surgery. If an injection site reaction does not improve within two weeks following the injection, or it worsens sooner than 2 weeks, the participant will be instructed to see his/her doctor. The dose of Vivitrol® (380mg) selected for this research has been studied in both normal healthy adults as well as in individuals who were using opioids, alcohol, and stimulants.

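### The risk sections give the liver exclusion as an unqualified protection, but eligibility waives it when no blood is drawn; no liver test is scheduled during dosing, and the waiver's scope is unclear

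*Combined protocol and SAP*

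**What the plan says.** **Eligibility.** Exclusion (1) in section 5.2 is "Liver function test levels greater than three times normal", followed by the note that "if a blood specimen is unable to be drawn the individual will not be excluded from participation". Section 5.8.9 repeats the note beside the test: "liver function tests (note: if a blood specimen is unable to be drawn the individual will not be excluded from participation), hepatitis profile". The synopsis (Subjects) words it differently: "if a blood sample is not obtained at baseline participants will still be eligible for participation". Exclusion (6), in both places, is "creatinine above normal limits", with no note about missing blood.

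**Risk protection.** Section 9.2.1, on protecting against raised liver enzymes, says "study applicants will be excluded if their liver enzymes are greater than triple the normal levels". It then adds that liver enzymes will be retested during the study and doses withheld where indicated. Section 5.7.4 mentions reports of raised enzymes and answers: "For this reason, we have an exclusion criterion regarding elevated liver function tests at baseline". Neither section mentions the waiver. Section 5.7.5 provides for linking participants to follow-up care when raised enzymes lead to discontinuation.

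**Schedule.** The Figure 3 row "Liver Function Tests, Hepatitis Profile" is ticked at baseline and, in the 6/7-month column, at month 7 only. Figure 3 has no creatinine row, and 5.8.9 does not list creatinine. Both state that they serve the inclusion and exclusion criteria. Section 5.3 requires laboratory tests to confirm eligibility before randomization but names none.

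**The concern.** The risk section tells the IRB and DSMB how participants are protected. Here it describes a screen that the eligibility section allows some participants to bypass, and it says nothing about them. These participants are prisoners, whom section 9.5 treats as vulnerable, and section 2.2 describes newly released inmates as being at raised risk of hepatitis B and C. Unknown liver status at the first injection is therefore a realistic situation in this trial.

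If baseline screening is bypassed, the remaining safeguard is the repeat testing promised in 9.2.1. That helps only if a test falls while doses can still be withheld.

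Two ambiguities add to this. Staff using the synopsis and staff using 5.2 may treat an inmate who declined or missed the draw differently. And no section says how exclusion (6) is judged when there is no specimen.

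**Working it through.** The plan states no figure to reproduce. The check compares the sections and then works out the timing.

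**1. A participant with no baseline blood specimen**

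| Source | What it implies |
|---|---|
| 5.2 and 5.8.9 | Eligible if the specimen could not be drawn |
| Synopsis, Subjects | Eligible if the sample was not obtained, for whatever reason |
| 9.2.1 | Liver risk is guarded by exclusion above triple normal; no exception given |
| 5.7.4 | The baseline liver exclusion is the response to the enzyme reports; no exception given |

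No result exists to compare with the threshold, so the exclusion cannot act. The protection described in 9.2.1 and 5.7.4 is absent for this participant.

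**2. Can the repeat test lead to a dose being withheld?**

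Inputs: prison injection 0 to 10 days before release (5.6.2); injections every 28 days (5.7.1); up to 37 days allowed between injections (5.7.3); one prison and six community injections (synopsis); next liver test at month 7 after release (Figure 3). A month is taken as 30.4 days.

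- Day of last injection after release = 6 × interval − (0 to 10).
- Day of month-7 test = 7 × 30.4 = 212.8, about day 213.
- On schedule: 6 × 28 = 168 days after the prison injection, which is day 158 to 168 after release.
- Gap from last injection to test: 213 − 168 = 45 days, to 213 − 158 = 55 days.
- Every interval stretched to the limit: 6 × 37 = 222, which is day 212 to 222, about the time of the test.
- In that extreme case the sixth of the seven injections falls at 5 × 37 = 185, which is day 175 to 185, still before the test.

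If months are counted as 28 days, the test falls at 7 × 28 = day 196, still after day 168. On-schedule dosing is therefore complete before the first scheduled post-baseline liver test. Even with maximal delay, only the seventh injection could be affected. This holds for every participant, but for a waived participant there is no baseline result either.

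**3. Waiver wording**

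The synopsis condition is met by refusal, a missed appointment or a technical failure. The condition in 5.2 and 5.8.9 is met only when blood could not be drawn. An inmate who declines or misses the draw is eligible under the first and unresolved under the second.

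**4. Creatinine**

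Three exclusions turn on a laboratory test: liver (1), creatinine (6) and pregnancy (7). Liver and pregnancy appear in 5.8.9 and Figure 3; creatinine appears in neither. Exclusion (6) needs the same specimen as exclusion (1), but the waiver is attached only to (1). With no specimen, one reader may say that (6) cannot be cleared and another that it is not triggered. The text does not settle this.

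**The case against.** The best defence is that nothing contradicts the waiver outright. It is stated openly in the synopsis, 5.2 and 5.8.9. Section 9.2.1 excludes people whose enzymes are above the threshold, and an untested person has no such result. Sections 9.2.1 and 5.7.4 are then incomplete summaries rather than opposing rules. Inmates whose blood is drawn are screened as described. Medical suitability and the exclusion for hazardous active illness apply without blood, and 9.1.1 says enzyme rises have not been reported at the injected dose.

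Most of this stands. It limits the expected harm and rules out the inference that 9.2.1 bars someone whom 5.2 admits. It does not make the risk sections accurate for a waived participant, and the repeat-testing promise does not fill the gap, because no test is scheduled during on-schedule dosing.

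Four stronger readings are tempting and are not supported:

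- **That nobody is tested for creatinine, so exclusion (6) never operates and all 240 go unscreened.** Section 5.3 promises unspecified laboratory tests that could include it, and the appendix forms are not available to check. Figure 3 also has no row for other exclusions such as BMI or suicidal ideation, so a missing row does not show that a criterion is ignored.
- **That the pilot shows how many would fail liver screening.** Its 20 of 74 (15 medical plus 5 medical and psychiatric, 27%) is not broken down by liver findings. Section 2.7.3 says most, if not all, of those excluded for medical or psychiatric reasons would be eligible here.
- **That a planned liver analysis is compromised.** None is planned: liver tests are not among the Figure 2 outcomes or in section 6.
- **That 5.2 and 9.2.1 give opposite eligibility decisions on liver grounds.** The only difference on eligibility is the waiver wording.

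**Conclusion.** The point holds as an inconsistency in safety and eligibility text. The liver protection in 9.2.1 and 5.7.4 is not true of participants admitted without blood. The repeat testing in 9.2.1, on which 5.7.5 also depends, is not supported by Figure 3: with 28-day dosing all seven injections precede the month-7 test by about 45 to 55 days. The waiver has two wordings of different breadth. For creatinine, the supportable statement is that no measures list or schedule names the test and that the waiver's reach is unstated.

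The number affected cannot be computed, because the documents give no rate of failed or missed draws. For scale only, each 5% of the 240 participants would be 0.05 × 240 = 12 people; any such rate is an assumption. The timing result assumes that Figure 3 is the complete liver-test schedule and that unscheduled tests are not routine. Power and the efficacy analysis are unaffected. The change should be made because it concerns participant safety and the rewording itself is cheap.

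**What to change.** Reconcile the synopsis (Subjects), 5.2, 5.3, 5.7.4, 5.7.5, 5.8.9, Figure 3 and 9.2.1 so that eligibility, risk protection and test schedule state the same rules. The reconciled text should:

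- use one wording for the waiver and say which circumstances it covers;
- say whether the waiver extends to creatinine, and make the creatinine exclusion agree with the lists of tests;
- make the repeat-testing statement in 9.2.1 and the schedule in Figure 3 agree;
- describe accurately, in 9.2.1 and 5.7.4, what protects any participant admitted without a specimen.

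The clinical rules themselves are for the study physician, IRB and DSMB to decide; this review does not propose them. In addition, record waiver status on the case report form and report the number by arm, so that the size of the issue becomes known.

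The cost is protocol wording, one case report form field, a stated protection that may read less favourably, and any additional tests or lost enrolment that those decisions entail.
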